### 3. PATIENT SELECTION

#### 3.1 Eligibility Criteria

3.1.1 Pathologically confirmed biliary tract cancer, having received at least 1 prior line of systemic therapy, and received no more than 2 prior lines of therapy in the metastatic setting (disease recurrence  $\leq$  6 months from the last dose of perioperative therapy/day of surgery [whichever is more recent] in resected patients will be considered the first line of therapy)

- Includes intrahepatic cholangiocarcinoma (IHC), extrahepatic cholangiocarcinoma (EHC), and gallbladder carcinoma (GBC), but not Ampulla of Vater cancers.

3.1.2 Patients must have measurable disease by RECIST v1.1

3.1.3 Age  $\geq$ 18 years. Because no dosing or adverse event data are currently available on the use of atezolizumab, cobimetinib, and CDX-1127 (varlilumab) in patients  $<$ 18 years of age, children are excluded from this study.

3.1.4 ECOG performance status  $\leq$ 1 (Karnofsky  $\geq$ 80%, see Appendix A).

3.1.5 Patients must have adequate organ and marrow function as defined below:

|                                      |  |
|--------------------------------------|--|
| - absolute neutrophil count          | $\geq$ 1,500/mcL   |
| - hemoglobin                         | $\geq$ 9.0 g/dL  |
| - platelets                          | $\geq$ 100,000/mcL   |
| - total bilirubin                    | $\leq$ 1.5 $\times$ institutional upper limit of normal (ULN) (Patients with known Gilbert disease who have serum bilirubin level $\leq$ 3 $\times$ ULN may be enrolled)   |
| - AST(SGOT)/ALT(SGPT)                | $\leq$ 3 $\times$ institutional ULN  |
| - Serum creatinine                   | $\leq$ 1.5 $\times$ institutional ULN
OR
$>$ 30 mL/min/1.73 m  (calculated by Cockcroft-Gault method) for patients with creatinine levels above institutional normal   |
| - creatinine clearance               | $\geq$ 3.0 g/dL  |
| - albumin                            | $\leq$ 1.5 $\times$ ULN
(This applies only to patients who do not receive therapeutic anticoagulation; patients receiving therapeutic anticoagulation, such as low-molecular-weight heparin or warfarin, should be on a stable dose) |
| - PT/aPTT                            | $<$ 5 $\times$ ULN   |
| - CK/CPK                             | $\geq$ 92% on room air   |
| - Oxygen saturation                  | $>$ 50%  |
| - Left Ventricular Ejection Fraction |  |

- 3.1.6 HIV-infected patients on effective anti-retroviral therapy with undetectable viral load within 6 months are eligible for this trial.
- 3.1.7 For patients with evidence of chronic hepatitis B virus (HBV) infection, the HBV viral load must be undetectable on suppressive therapy, if indicated.
- 3.1.8 Patients with a history of hepatitis C virus (HCV) infection must have been treated and cured. For patients with HCV infection who are currently on treatment, they are eligible if they have an undetectable HCV viral load.
- 3.1.9 Patients must be willing to undergo 2 sets of core needle biopsies. If possible, biopsied sites should be different than those used for measurable disease/RECIST measurements, but this is not mandatory.
- 3.1.10 Patients must have an estimated life expectancy of greater than 3 months.
- 3.1.11 Patients must be able to swallow pills
- 3.1.12 Patients should not have evidence of retinal pathology on ophthalmologic examination; or neurosensory retinal detachment, RVO, or neovascular macular degeneration.
- 3.1.13 The effects of atezolizumab, cobimetinib, and CDX-1127 (varlilumab) on the developing human fetus are unknown. For this reason, women of child-bearing potential and men must agree to use adequate contraception (hormonal or barrier method of birth control; abstinence) prior to study entry, for the duration of study participation, and 5 months after the last dose of Atezolizumab. Should a woman become pregnant or suspect she is pregnant while she or her partner is participating in this study, she should inform her treating physician immediately. Men treated or enrolled on this protocol must also agree to use adequate contraception prior to the study, for the duration of study participation, and 5 months (150 days) after completion of atezolizumab, cobimetinib, and CDX-1127 (varlilumab) administration.
- 3.1.14 Ability to understand and the willingness to sign a written informed consent document.

## 3.2 Exclusion Criteria

- 3.2.1 Patients with prior allogeneic bone marrow transplantation within the past 5 years or prior solid organ transplantation at any point.
- 3.2.2 Patients who have had chemotherapy or radiotherapy within 4 weeks (6 weeks for nitrosoureas or mitomycin C) prior to entering the study or those who have not recovered from adverse events (other than alopecia or neuropathy) due to agents administered more than 4 weeks earlier. However, the following therapies are allowed:
  - Hormone-replacement therapy or oral contraceptives
  - Herbal therapy >1 week prior to Randomization (herbal therapy intended as

- anticancer therapy must be discontinued at least 1 week prior to Randomization)
- Palliative radiotherapy for bone metastases >2 weeks prior to Randomization

3.2.3 Prior treatment with anti-CTLA-4, anti-PD-1, or anti-PD-L1 or other immune checkpoint inhibitor therapeutic antibodies or pathway-targeting agents with the following exceptions:

- Patients who have only received previous durvalumab (anti-PD-L1) as part of first line in combination with gemcitabine and cisplatin (TOPAZ-1 regimen [NCT03875235]) **are eligible.**
- Patients who have only received previous pembrolizumab (anti-PD-1) as part of first line in combination with gemcitabine and cisplatin (KEYNOTE-966 regimen [NCT04003636]) **are eligible.**

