### 9.2 Sample Size/Accrual Rate

The study is planned for 64 evaluable subjects (32 subjects per treatment arm). The objective response rate (ORR) of BTCs treated with FOLFOX, anti-PD-1 monotherapy or anti-PDL1+MEKi is around 5%. A clinically meaningful improvement that warrants further study would be a 20% ORR. A Simon two-stage minimax design is planned for each arm. Arm specific type I error is set at 0.1 (one-sided) when evaluating the co-primary endpoints of ORR and PFS. For each arm, 18 patients will be enrolled in the first stage. If none have OR, the accrual to that arm will be terminated. If 1 or more respond, then additional 14 patients will be enrolled (for a total of 32 patients in that arm). If 4 or more patients achieve OR (12.5%) in stage 1 and stage 2 combined, the endpoint is met in that arm. The design yields at least 90% power to detect a true

response rate of at least 20%, with at least .90 probability of a negative result (no more than 3 responses if the true response rate is no more than 5%, for each of the two arms. The chance of early stopping after stage 1 in each arm is 0.4 when the true response rate is 5%.

If both arms meet the response endpoint criteria, the comparison of PFS will be performed. The median progression free survival of BTCs treated with FOLFOX, anti-PD-1 monotherapy, & anti-PDL1+MEKi is 4.0, 2.0, and 3.5 months, respectively. Randomization of 64 patients, with observation of 55 PFS events would yield 90% power to detect an HR = 0.5 (corresponding to 3.5 vs. 7 months median PFS in the doublet and triplet arm, respectively), at the one-sided 0.10 significance level. An observed 40% increase in median PFS for the triplet arm (approximately 1.4 months, assuming an approximately 3.5-month median PFS in the doublet arm; observed HR=0.714) would be sufficient to achieve statistical significance.

Taking into account dropout/study attrition, we anticipate screening between 70-80 patients in order to achieve 32 evaluable patients per treatment arm (N=64) with an anticipated accrual rate of 4 patients/month.

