### 9.3 Stratification Factors

#### Site of disease (1 level of stratification with 3 categories):

After the screening phase, eligible subjects will undergo stratified randomization according to the site of disease: 1) gallbladder cancer (GBC); 2) intrahepatic (IHC); and 3) extrahepatic cholangiocarcinoma (EHC) to ensure similar distribution of BTCs subtypes across treatment arms. There will be no further stratification based on other patient or tumor characteristics (such as age, sex) in this trial. Sample size calculations were performed without stratification, as the sample size is small.

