|   | D: For patients randomized to atezolizumab and CDX-1127 (varilumab) plus cobimetinib ( study arm A only ). Dosing as follows: cobimetinib 60 mg daily (21 days on/7 days off). On Days 1 and 15 of each cycle, cobimetinib should be taken before receiving atezolizumab and CDX-1127 (varilumab). Cobimetinib should be taken in the morning at the same time every day. It can be taken with or without food. If a dose of cobimetinib is not taken within 4 hours of the scheduled dose, it should be considered missed and not taken. Resume dosing at the next scheduled dose/time. If unable to take dose prior to infusion, patient may still take that day's dose as long as it is within 4 hours of regularly scheduled time, otherwise it should be considered missed and not taken with dosing resumed at the next scheduled day/time. |                     |        |        |         |       |        |                    |        |       |  |
|   | E: Includes history of lung disease, HIV, hepatitis B or C infection, and complete cancer history, including primary site of cancer, gross location of primary tumor, secondary sites of cancer, histology, histologic grade, date of initial diagnosis, date of metastatic diagnosis, and prior cancer therapy regimens.  |                     |        |        |         |       |        |                    |        |       |  |
|   | F: Complete physical exam will be completed at baseline; focused physical examinations will be conducted thereafter. Physical examinations should be performed within a window of up to 7 days prior to dosing on Days 1 and 15 of Cycle 1 and Day 1 for all subsequent cycles.  |                     |        |        |         |       |        |                    |        |       |  |
|   | G: For the first infusion, the patient's vital signs (heart rate, respiratory rate, blood pressure, and temperature) should be determined within 60 minutes before, during (every 15 [±5] minutes), and 30 (±10) minutes after the infusion. For subsequent infusions, vital signs will be collected within 60 minutes before and within 30 minutes after the infusion. Vital signs should be collected during the infusion only if clinically indicated.  |                     |        |        |         |       |        |                    |        |       |  |

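### Prior PD-(L)1 exposure is allowed at entry but enters neither the randomisation nor the PFS comparison, so a chance imbalance between arms would go uncorrected

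*Combined protocol and SAP*

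**What the plan says.** - **Eligibility.** Section 3.1.1 requires patients "having received at least 1 prior line of systemic therapy". Section 3.2.3 excludes earlier checkpoint inhibitor treatment, with two exceptions. The first is "Patients who have only received previous durvalumab (anti-PD-L1) as part of first line in combination with gemcitabine and cisplatin". The second is "Patients who have only received previous pembrolizumab (anti-PD-1) as part of first line in combination with gemcitabine and cisplatin".
- **Treatment.** Both arms receive atezolizumab (6.1), so these patients are treated again on the PD-1/PD-L1 axis.
- **Randomisation.** Section 9.3 stratifies by site of disease and adds: "There will be no further stratification based on other patient or tumor characteristics (such as age, sex) in this trial".
- **PFS comparison.** Sections 9.1 and 12.1.6 specify log-rank tests between arms and name no stratum or covariate. Under 9.2 the comparison is made only if both arms meet the response criterion.
- **Error rate and ORR target.** "Arm specific type I error is set at 0.1 (one-sided) when evaluating the co-primary endpoints of ORR and PFS". One null rate (5%) and one target apply to everyone: "A clinically meaningful improvement that warrants further study would be a 20% ORR".
- **Data.** Footnote E of the Study Calendar (Section 11) includes in the baseline history "and prior cancer therapy regimens", so prior exposure can be derived for every patient.

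No analysis by prior PD-(L)1 exposure is planned. Adjustment for covariates appears only in the pharmacokinetic Cox models, the exploratory marker-response models (9.4, 9.4.1) and the modelling of toxicity (9.5.1).

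**The concern.** The plan excludes prior checkpoint treatment as a class and then admits two defined groups who have had it, so it treats exposure as relevant at entry and ignores it afterwards. Both regimens contain a PD-L1 antibody, and exposure may plausibly be related to PFS. With 32 patients per arm and no balancing, the arms can differ by several exposed patients by chance. If exposure is prognostic, the unadjusted log-rank test then favours one arm for a reason unrelated to cobimetinib. Whoever reads the result would see the imbalance in the baseline table but have no pre-specified analysis that accounts for it. Any adjustment would be post hoc.

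**Working it through.** **Reproducing the plan's figures.** For the two-stage rule (stop at 0 of 18; success at 4 or more of 32), exact binomial sums give power 0.9015 at 20%, type I error 0.0721 at 5%, and early stopping 0.95^18 = 0.397. For PFS, Schoenfeld's formula gives 4 × (1.2816 + 1.2816)² / (ln 0.5)² = 26.28 / 0.4805 = 54.7, so 55 events. Both match 9.2.

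**Inputs not in the documents (assumptions).** Exposed share f = 50%; PFS hazard ratio for exposed versus naive patients 1.5 to 2.0.

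**How often the arms differ.** At f = 0.5 the difference in exposed counts has SD √(64 × 0.25) = 4. With continuity correction, P(5 or more fewer in the triplet arm) = P(Z < −4.5/4) = 0.13, and 0.26 in either direction.

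**Effect by hand, at exactly 5 fewer.** The imbalance is 5/32 = 0.156. The log hazard ratio shifts by about 0.156 × ln(HR), and its standard error at 55 events is 2/√55 = 0.270.
- HR 1.5: shift 0.063, or 0.235 SE. One-sided error P(Z > 1.282 − 0.235) = 0.15.
- HR 2.0: shift 0.108, or 0.402 SE. Error P(Z > 0.880) = 0.19.

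**Simulation.** 6,000 runs; 64 patients, 32 per arm; exponential PFS with a 3.5-month doublet median; analysis at 55 events; no site strata; not conditioned on the ORR gate. Entries are plain log-rank / log-rank stratified by exposure.

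| Rejection rate | Prognostic HR 1.5 | Prognostic HR 2.0 |
|---|---|---|
| No triplet effect, all runs | 0.094 / 0.096 | 0.106 / 0.107 |
| No triplet effect, triplet 5+ fewer exposed | 0.153 / 0.102 | 0.226 / 0.116 |
| No triplet effect, triplet 5+ more exposed | 0.049 / 0.103 | 0.028 / 0.099 |
| Triplet HR 0.5, all runs | 0.888 / 0.894 | 0.859 / 0.887 |
| Triplet HR 0.5, triplet 5+ more exposed | 0.844 / 0.903 | 0.707 / 0.867 |

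The conditional rows rest on about 0.13 × 6,000 = 780 runs, with a standard error of about √(0.2 × 0.8/780) = 0.014. A repeat of the same simulation with 100,000 runs puts the conditional plain log-rank error at 0.17 (HR 1.5) and 0.21 (HR 2.0), and the stratified error at about 0.10. I therefore quote about 0.15 to 0.21.

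**If exposure is not prognostic.** Power is 0.895 plain and 0.893 stratified here; the larger run puts the loss at about 1 point.

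**If the triplet works less well in exposed patients** (HR 0.5 in naive patients, no prognostic effect), power is 0.696 plain and 0.671 stratified when the HR in exposed patients is 0.75, and 0.514 and 0.461 when it is 1.0. Stratifying does not recover this loss.

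**The case against.** **The size rests on assumptions.** This is true. The documents give no exposed share and no effect of exposure. Section 2.1 puts PD-(L)1 monotherapy response in biliary cancer at about 5 to 11%, so most naive patients would not respond to PD-L1 blockade alone, and exposure may separate patients only weakly. If it is not prognostic, there is nothing to correct.

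**The log-rank test is valid as planned.** This also stands. Over all randomisations its error stays near 0.10. The issue is precision and bias conditional on an imbalance that can be observed.

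**The shift is modest.** At f between 30% and 70% and a prognostic HR of 1.3 to 2.0, the 95% range of imbalance moves the PFS hazard ratio by a factor of up to 1.06 to 1.19. The gap between the design HR of 0.5 and the critical HR of 0.708 is ln(0.708/0.5) = 0.348; ln(1.19) = 0.174 is half of it. An imbalance would rarely decide the trial alone.

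**A reader might infer that admitting these patients invalidates the 90% ORR power.** It does not. Section 9.2 states that power for a true response rate of at least 20% in the enrolled population, and it reproduces. Lower power at 17%, 15% or 13% (0.81, 0.72, 0.60) is how any design behaves below its target, and nothing in the documents says that exposed patients respond less often.

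**A reader might also take these patients to have failed PD-(L)1 treatment.** Section 3.2.3 requires only that they received it.

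**Results by exposure can be tabulated anyway.** They can, because prior regimens are recorded. What is missing is the commitment before the data are seen.

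**Conclusion.** The gap is real and moderate. A baseline factor that the eligibility criteria themselves single out, and that is already recorded, plays no part in the randomisation or the PFS comparison. With half the patients exposed and a prognostic HR of 1.5 to 2.0, about 13% of randomisations leave the triplet arm with at least 5 fewer exposed patients; the one-sided error is then about 0.15 to 0.21 instead of about 0.10. The mirror-image imbalance costs power: at HR 2.0, 0.707 against 0.867 with stratification. Averaged over all randomisations, type I error is unaffected and adjustment gains at most about 2 to 3 points of power.

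The documents do not support the stronger readings that the trial is underpowered because of these patients, or that the log-rank test is invalid. Nor would adjustment rescue power if cobimetinib adds less in exposed patients.

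**What to change.** In 9.1 and 12.1.6, pre-specify a PFS comparison adjusted for prior PD-(L)1 exposure (yes/no), either as a covariate in a Cox model or as a stratum in the log-rank test. State in advance whether this or the plain log-rank is the deciding test, so that only one test decides and the other is supportive. Report ORR with exact confidence intervals by prior exposure in each arm, labelled descriptive. Section 9.2 needs no correction on this point.

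The cost is SAP wording and a variable derived from data already collected; sample size, eligibility and randomisation do not change. The downsides are one degree of freedom with 55 events, about 1 point of power if exposure is not prognostic, and wide subgroup intervals. With 16 exposed patients in an arm, 0 of 16 has an exact 95% upper limit of 1 − 0.025^(1/16) = 21%, which still includes the 20% target.

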3.2.4 Prior treatment with MEK or ERK inhibitors

3.2.5 Treatment with any other investigational agent within 4 weeks prior to Randomization.

3.2.6 Treatment with systemic immunostimulatory agents (including, but not limited to, interferon [IFN]- $\alpha$  or interleukin [IL]-2) within 6 weeks prior to Randomization.

3.2.7 Treatment with systemic immunosuppressive medications (including, but not limited to, prednisone ( $>10$ mg), cyclophosphamide, tacrolimus, sirolimus, azathioprine, methotrexate, thalidomide, and anti-tumor necrosis factor [anti-TNF] agents) within 2 weeks prior to Randomization.

- Patients who have received acute, low dose, systemic immunosuppressant medications (e.g., a one-time dose of dexamethasone for nausea) may be enrolled.
- The use of physiologic doses of systemic corticosteroids and mineralocorticoids (e.g., fludrocortisone) for patients with orthostatic hypotension or adrenocortical insufficiency is allowed.
- The use of topical and inhaled corticosteroids are allowed due to low systemic absorption.

3.2.8 Patients taking bisphosphonate therapy for symptomatic hypercalcemia. Use of bisphosphonate therapy for other reasons (e.g., bone metastasis or osteoporosis) is allowed.

3.2.9 Presence of therapeutically actionable mutation with approved targeted therapy (e.g. FGFR fusion patients are eligible for study therapy in the 3rd line setting). Patient must have received somatic mutation testing (tissue or liquid) prior to enrollment.

3.2.10 Clinically significant ascites (palpable on exam, paracentesis in last 3 months, and/or symptomatic).

3.2.11 Patients with known primary central nervous system (CNS) malignancy or symptomatic CNS metastases are excluded, with the following exceptions:

- Patients with asymptomatic treated CNS metastases may be enrolled, provided all

the criteria listed above are met as well as the following:

- Radiographic demonstration of improvement upon the completion of CNS-directed therapy and no evidence of interim progression between the completion of CNS-directed therapy and the screening radiographic study
- No stereotactic radiation or whole-brain radiation within 28 days prior to Randomization
- Screening CNS radiographic study  $\geq 4$  weeks from completion of radiotherapy and  $\geq 2$  weeks from discontinuation of corticosteroids
- Follow-up brain imaging 3 months after central nervous system (CNS)-directed therapy shows no evidence of progression

3.2.12 History of malignant bowel obstruction.

3.2.13 History of severe allergic, anaphylactic, or other hypersensitivity reactions to Chinese hamster ovary cell products, chimeric, humanized, or other recombinant human antibodies or fusion proteins

3.2.14 History of allergic reactions attributed to compounds of similar chemical or biologic composition to atezolizumab, cobimetinib, or CDX-1127 (varlilumab).

3.2.15 Patients receiving any medications or substances that are considered moderate to strong inhibitors or inducers of CYP3A and are not able to switch to an alternative that minimizes interaction potential will be ineligible. Coadministration of cobimetinib with a strong CYP3A4 inhibitor can increase cobimetinib systemic exposure significantly (e.g. itraconazole increased serum systemic cobimetinib exposure by 6.7 fold). On the other end, coadministration of cobimetinib with a strong CYP3A inducer may decrease cobimetinib systemic exposure by more than 80% thus reducing its efficacy. Because the lists of these agents are constantly changing, it is important to regularly consult a frequently-updated list such as <http://medicine.iupui.edu/clinpharm/ddis/>; medical reference texts such as the Physicians' Desk Reference may also provide this information. As part of the enrollment/informed consent procedures, the patient will be counseled on the risk of interactions with other agents, and what to do if new medications need to be prescribed or if the patient is considering a new over-the-counter medicine or herbal product. Appendix C should be presented to patient.

- Patients on mild inhibitors or inducers of CYP3A are allowed.

3.2.16 Patients with a known clinically significant liver disease, including active viral, alcoholic, or other hepatitis; cirrhosis; fatty liver; and inherited liver disease.

- Patients with past or resolved hepatitis B infection (defined as having a negative hepatitis B surface antigen [HBsAg] test and a positive anti-HBc [antibody to hepatitis B core antigen] antibody test) are eligible.
- Patients positive for hepatitis C virus (HCV) antibody are eligible only if polymerase chain reaction (PCR) is negative for HCV RNA.

3.2.17 Patients who have received immunosuppressive treatment for systemic autoimmune disease, including, but not limited to, systemic lupus erythematosus, rheumatoid arthritis,

inflammatory bowel disease, vascular thrombosis associated with antiphospholipid syndrome, Wegener's granulomatosis, Sjögren's syndrome, multiple sclerosis, vasculitis, or glomerulonephritis within the last 2 years.

- Patients with a history autoimmune endocrine disorders on stable doses of physiologic hormone replacement may be eligible.
- Patients with controlled Type 1 diabetes mellitus on a stable insulin regimen may be eligible.
- Patients with eczema, psoriasis, lichen simplex chronicus or vitiligo with dermatologic manifestations only (e.g., patients with psoriatic arthritis would be excluded) are permitted provided that they meet the following conditions:
  - Patients with psoriasis must have a baseline ophthalmologic exam to rule out ocular manifestations
  - Rash must cover less than 10% of body surface area (BSA)
  - Disease is well controlled at baseline and only requiring low potency topical steroids (e.g., hydrocortisone 2.5%, hydrocortisone butyrate 0.1%, flucinolone 0.01%, desonide 0.05%, aclometasone dipropionate 0.05%)
  - No acute exacerbations of underlying condition within the last 12 months (not requiring psoralen plus ultraviolet A radiation [PUVA], methotrexate, retinoids, biologic agents, oral calcineurin inhibitors; high potency or oral steroids)
  - Patients with history Guillain-Barré syndrome or myasthenia gravis at any point will not be eligible.

3.2.18 History of idiopathic pulmonary fibrosis, pneumonitis (including drug induced), organizing pneumonia (*i.e.*, bronchiolitis obliterans, cryptogenic organizing pneumonia, etc.), or evidence of active pneumonitis on screening chest computed tomography (CT) scan. History of radiation pneumonitis in the radiation field (*fibrosis*) is permitted.

3.2.19 Patients with active tuberculosis (TB) are excluded.

3.2.20 Severe infections within 4 weeks prior to Randomization, including, but not limited to, hospitalization for complications of infection, bacteremia, or severe pneumonia.

3.2.21 Signs or symptoms of infection within 2 weeks prior to Randomization.

3.2.22 Received oral or intravenous (IV) antibiotics within 2 weeks prior to Randomization.

3.2.23 Patients receiving prophylactic/suppressive antibiotics will not be eligible.

3.2.24 Major surgical procedure within 28 days prior to Randomization or anticipation of need for a major surgical procedure during the course of the study.

3.2.25 Administration of a live, attenuated vaccine within 4 weeks before Randomization or anticipation that such a live, attenuated vaccine will be required during the study and up to 5 months after the last dose of atezolizumab.

- Influenza vaccination should be given during influenza season only

(approximately October to March). Patients must not receive live, attenuated influenza vaccine within 4 weeks prior to Randomization or at any time during the study.

- COVID-19 vaccination is not exclusionary but should be administered at least 7 days before study start.

3.2.26 Patients with psychiatric illness/social situations that would limit compliance with study requirements.

3.2.27 Pregnant women are excluded from this study because one or more study agents have the potential for teratogenic or abortifacient effects. Because there is an unknown but potential risk for adverse events in nursing infants secondary to treatment of the mother with atezolizumab, cobimetinib, and CDX-1127 (varlilumab), breastfeeding should be discontinued if the mother is treated with atezolizumab, cobimetinib, and CDX-1127 (varlilumab).

3.2.28 Patients who are using ethinyl estradiol containing oral contraceptives when administered concomitantly with cobimetinib, are excluded due to increased risk of venous thromboembolism.

3.2.29 Patients with a history of clinically significant cardiac dysfunction, including the following:

- **Left ventricular ejection fraction (LVEF) below institutional LLN or below 50%, whichever is lower**
- Current unstable angina
- Current symptomatic congestive heart failure (CHF) of New York Heart Association class 2 or higher
- Uncontrolled hypertension  $\geq$ Grade 2 (patients with a history hypertension controlled with anti-hypertensives to  $\leq$ Grade 1 are eligible).
- Uncontrolled arrhythmias
- Myocardial infarction, severe/unstable angina, symptomatic CHF, cerebrovascular accident or transient ischemic attack within the previous 6 months
- History of treatment with cardiotoxic agents

